11.8. Compliance with the protocol

The study doctor conducts the study in accordance with the approved Protocol.

Deviation from the Protocol is any change, inconsistency, or deviation from the study design or the study procedures described in the Protocol.

Any deviation from the Protocol during the clinical study should be recorded and reflected in the study documentation.

All deviations from the Protocol are classified as significant or minor.

A minor deviation from the protocol does not significantly affect the rights, safety and well-being of the patient or completeness, accuracy, and reliability of the study data.

A significant deviation from the protocol (or violation of the protocol) is a deviation that may affect the rights, safety and well-being of the patient or completeness, accuracy, and reliability of the study data.

Examples of significant deviations from the protocol:

- the patient met the withdrawal criteria, but was not excluded from the study,
- the patient was included in the study while not being eligible,
- conducting study procedures without a written informed consent of the patient,
- violations of the procedure for administration of the investigational product,
- lack of discipline of the patient, non-compliance with limitations implied by the study,
- systematic (repeated at least 2 times) negligent loss of data or samples collected for the study in the centre,
- the patient missed a visit.

Significant deviations must be reported to the ethics committee. If significant deviations from the protocol are detected, the patient should be excluded from the final analysis of efficacy data.

If the visit procedures go beyond the time frames specified by the protocol, the Sponsor will consider continued patient participation in the study at the request of the study doctor on an individual basis.

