9.6. Population for analysis

The following populations will be used for analysis:

1. All enrolled patients (Intent-to-treat, ITT).
2. Safety population: Patients who received at least one infusion, according to the prescribed treatment.

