9.7.2. Statistical methods for efficacy analysis

ITT will be the main population for efficacy analysis.

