9.7.3. Statistical methods for analysis of safety of the investigational product

Safety analysis will be performed in the safety population. Regardless of the reason for the completion of the study, the data of all patients who received at least one infusion according to the assignments will be included in the safety analysis.

Safety data will be analysed using the methods chosen for efficacy analysis.

Incidences of adverse events/serious adverse events will be calculated for assessment of AEs. Incidences of adverse events reported during the study will be presented as number of patients with AE in total and in each treatment group. Also, number of AEs per each severity category and per causal relationship with the study drug will be presented.

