9.10. Procedures that increase accuracy of the statistical analysis

Monitors will check the case report forms for missing data during monitoring visits to the centre. If any data are absent in the CRF and are present in the source records, relevant inquiries and instructions for the corrective actions will be sent to the study doctors.

The statistician and the Principal Investigator will review the database for any doubtful, missing, and non-analysable data. Inquiries will be sent to the investigators in case of any findings.

If necessary, the study doctors will correct the errors in CRFs and inform the Principal Investigator and the monitors about the corrective actions. If the identified errors in the data cannot be corrected after the completion of the subjects' participation in the study, sensitivity of the resulting parameters to questionable data will be performed as part of the statistical analysis. Information about any missing, doubtful, and non-analysable data will be presented in the Clinical Study Report.

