11.9. Final study report

A medical research expert/medical consultant will be involved in preparation of the observational study report. The discussion of the results and conclusions will include a clear conclusion on the safety profile as well as efficacy of the investigational products.

The observational study report will show the number and type of Protocol Amendments (if applicable), the number of violations and deviations from the Protocol found during the study.

The final version of the report will be signed by the ones who prepared it, a medical research expert/medical consultant, the head of this study, and will be approved by the head of the institution and certified with the seal of the institution.

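### Sections 9.6 and 9.7.2 analyse all enrolled patients for efficacy, section 11.8 excludes those with significant deviations, and nothing says which rule prevails

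*Combined protocol and SAP*

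**What the plan says.** Section 9.6 lists two analysis sets. The first is "All enrolled patients (Intent-to-treat, ITT"; the second is a safety set of patients given at least one infusion. Section 9.7.2 then states: "ITT will be the main population for efficacy analysis".

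Section 11.8, in the quality-control chapter, splits deviations into minor and significant, gives seven examples of significant ones, and adds: "If significant deviations from the protocol are detected, the patient should be excluded from the final analysis of efficacy data". Two of the examples are "the patient missed a visit" and "the patient met the withdrawal criteria, but was not excluded from the study". Others are breaches of the administration procedure and patient non-compliance. The missed-visit item has no minimum number, whereas the data-loss item in the same list requires at least two occurrences.

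Three other sections bear on who is analysed:

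- Section 5.4 leaves undosed patients who leave the study out of the statistical analysis.
- Section 9.4 substitutes no missing values and leaves missing data out of the analysis.
- Section 9.7.3 settles the matter for safety, whatever the reason a patient's participation ended: "the data of all patients who received at least one infusion according to the assignments will be included in the safety analysis". Section 9.7.2 has no matching sentence for efficacy.

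**The concern.** A patient with a significant deviation cannot be both in the main efficacy analysis and excluded from it. An analyst working from chapter 9 keeps that patient; one working from 11.8 removes the patient. Both would be following the protocol, and their Day 15 results could differ.

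The choice matters because several of the listed deviations can arise after enrolment: a withdrawal criterion met without withdrawal, an administration breach, non-compliance and a missed visit. Such events can be related to how the patient is doing. The study is open and has a single group, so no control arm undergoes the same exclusions and any selection passes straight into the reported result. Section 5.5 rules out replacing withdrawn patients. If the choice of set is left until outcomes are known, it can also be questioned as data-driven.

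**Working it through.** **Which rule governs.** The sections that might settle it do not:

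- 9.6 defines no per-protocol set to which the exclusion in 11.8 could belong.
- 9.3, whose heading mentions protocol violations, only allows statistical methods to be replaced.
- 9.4 deals with missing values, not with removing patients.
- 9.10 promises disclosure: "Information about any missing, doubtful, and non-analysable data will be presented in the Clinical Study Report". 11.9 promises a count: "the number of violations and deviations from the Protocol found during the study". Neither says who is analysed.
- The last paragraph of 11.8 sends out-of-window procedures to the sponsor case by case, but on continued participation, not on the analysis set.

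**Where the rules differ for the primary endpoint.** Under 9.4 a patient with no Day 15 value is absent from the Day 15 analysis whichever rule is used. The missed-visit example therefore separates the rules only when another visit was missed and Day 15 was observed.

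**Size, as an illustration.** The only design figure is the minimum of 50 patients in the synopsis. It comes with no effect size, variability, power or drop-out, so there is no calculation to reproduce. Assume all 50 have a Day 15 value, x of them lie on one side of a chosen cut of the 7-point scale, and 11.8 excludes k. No responder definition is needed.

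- ITT share: x/50.
- 11.8 share if all k excluded lie on the other side: x/(50−k). Gap: x/(50−k) − x/50 = kx/[50(50−k)].
- 11.8 share if all k excluded lie on the same side: (x−k)/(50−k). Gap: x/50 − (x−k)/(50−k) = k(50−x)/[50(50−k)].
- Largest gap: k·max(x, 50−x)/[50(50−k)].

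When at least k patients lie on each side, max(x, 50−x) ≤ 50−k, so the gap cannot exceed k/50.

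| k (assumed) | Largest gap at x = 25 | Ceiling k/50 |
|---|---|---|
| 1 | 1/98 = 1.0 points | 2 points |
| 2 | 2/96 = 2.1 points | 4 points |
| 5 | 5/90 = 5.6 points | 10 points |
| 10 | 10/80 = 12.5 points | 20 points |

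Check at k = 5, x = 25: ITT gives 50.0%; 11.8 gives 25/45 = 55.6% or 20/45 = 44.4%. At k = 5, x = 40: ITT gives 80.0%; 11.8 gives 40/45 = 88.9% or 35/45 = 77.8%, a gap of at most 8.9 points.

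For the mean change on the scale, let d be the mean change in retained patients minus that in excluded patients. The retained mean differs from the mean of all 50 by kd/50. For assumed d of 1 to 3 points this is 0.1 to 0.3 points at k = 5 and 0.2 to 0.6 points at k = 10.

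**What values of k are conceivable.** Table 1 has six fixed post-baseline days (3, 5, 7, 11, 15, 29). With an assumed independent miss probability p per visit, the expected number with any missed visit is 50[1 − (1−p)^6]. Of these, 50p lack Day 15 and drop out anyway. At p = 2% this is 5.7 − 1.0 = 4.7 patients; at p = 5% it is 13.2 − 2.5 = 10.7. These cover the missed-visit item alone and rest entirely on the assumed p.

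**The case against.** The best defence is that 11.8 is a misplaced per-protocol rule. Section 9.7.2 calls ITT the main population, which leaves room for supplementary efficacy analyses, and 11.8 says only that the patient should be excluded. That may be what was meant, but the text refers to the final analysis of efficacy data and no per-protocol set exists, so the reading cannot be confirmed from the document.

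It can also be said that analysts may differ anyway, because 9.1 and 9.7.2.1 name no test or estimator for the primary endpoint. That is true, but it is a separate gap and does not settle who is analysed.

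Other mitigation stands. Section 6.2 and the notes to Table 1 allow visits by telephone or other remote means, so a completed remote contact need not count as missed. The data-loss example describes a failure of the centre and may not lead to exclusion of individual patients.

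Three stronger readings are tempting but unsupported:

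- A reader might take k/(50−k), which is 11.1 points at k = 5 and 25.0 at k = 10, as the disagreement. That is the distance between two opposite extremes under 11.8 alone. The disagreement at issue is between ITT and 11.8, and it is smaller.
- A reader might infer that 11.8 would flatter the drug. Patients doing badly could be excluded, but so could patients discharged early who then miss visits. The documents do not determine the net direction.
- A reader might infer that outcomes are lost once a patient withdraws. Section 13.4 has the eCRF filled in up to withdrawal, but 4.3 provides for collecting the latest data, 4.5 and 5.4 for continued outcome collection, 5.3 and 5.6 for follow-up of adverse events, and 6.1 for an Early Termination Visit with Day 29 scope.

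**Conclusion.** The plan is wrong as written: it gives two incompatible rules for who enters the final efficacy analysis and does not rank them. This conclusion rests on the text alone. Its numerical effect cannot be known from the documents. At most k/50 separates the two results at any scale cut with at least k patients on each side, and the gap reaches its maximum only if every excluded patient lies on one side. The values of k, x, d and p above are assumed, and 50 is a minimum.

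The rule in 5.4 on undosed patients is a second, smaller mismatch with an all-enrolled set. Few patients should be affected, since 6.2 places enrolment and the first administration on the same day.

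**What to change.** - In 9.6 and 9.7.2, name one primary efficacy set, either all enrolled or all dosed patients, and state that it prevails over 11.8. Make 5.4 agree with it.
- In 11.8, confine the deviation exclusions to a per-protocol set defined in 9.6 and used only for sensitivity analysis. Require deviations to be classified before outcomes are analysed.

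The cost is a written amendment, local ethics approval under 11.7 because the change bears on scientific value, and one extra sensitivity table.

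Further rules on outcome collection after withdrawal, and best-case and worst-case bounds for unknown Day 15 status, are optional and separate. Sections 4.3, 4.5, 5.3, 5.4, 5.6 and 6.1 already provide part of the follow-up.

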5.3 Withdrawal criteria

1. The investigator decided that withdrawal from the study is in the patient's interests.
2. Withdrawal of the informed consent (the patient does not want to continue participation in the study).
3. Serious deviation from the study protocol.
4. Idiosyncrasy to the investigational products that developed during the treatment period.
5. AE/SAE that requires an examination and/or treatment that would affect the study procedures significantly.
6. Patient non-compliance.
7. The patient was enrolled by mistake.
8. The patient receives/needs an additional treatment that could affects result of the study or the patient safety.
9. Other conditions or events that require patient withdrawal, as judged by the study

doctor.

The subjects that were withdrawn from the study because of an AE/SAE will be followed until the AE/SAE is resolved or the patient is stabilized.

A subject will be considered lost to follow-up if he or she fails to appear for a follow-up assessment and cannot be contacted with good effort. These efforts will be documented in the subject's record.

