9.3. Review of violations from the protocol and plan of analysis

Statistical methods could be replaced if it contributes to a more correct and informative analysis. Any changes will be described and justified in the final study report.

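### Section 11.8 removes patients with significant deviations from the final efficacy analysis, Sections 9.6 and 9.7.2 keep all enrolled patients in it, and nothing says which rule prevails

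*Combined protocol and SAP*

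**What the plan says.** Two parts of the combined protocol and SAP give instructions on who enters the efficacy analysis.

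- **Statistics.** Section 9.6 lists two analysis sets. The first is "All enrolled patients (Intent-to-treat, ITT"; the second is the safety population. Section 9.7.2 adds: "ITT will be the main population for efficacy analysis".
- **Compliance.** Section 11.8 says: "If significant deviations from the protocol are detected, the patient should be excluded from the final analysis of efficacy data". It defines a significant deviation broadly, as one that may affect a patient's rights, safety or well-being, or the completeness, accuracy or reliability of the data. Its examples include "the patient met the withdrawal criteria, but was not excluded from the study", "violations of the procedure for administration of the investigational product", enrolment of an ineligible patient, study procedures without written consent, and one missed visit.

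Three other sections bear on this. Section 9.3 mentions protocol violations in its heading, but its content is about methods: "Statistical methods could be replaced if it contributes to a more correct and informative analysis". Section 9.4 says missing data are neither replaced nor considered. Section 5.4 leaves out of the statistical analysis any patient who leaves the study without receiving a dose.

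**The concern.** A patient with a significant deviation is inside the efficacy analysis under 9.7.2 and outside it under 11.8. The analyst has to choose, and the plan does not say how.

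The study is open and single-group (4.2, 4.3.1), with at least 50 patients. Unless deviations are classified early, the choice of rule, and the decision on which deviations are significant, can be made by people who already know the Day 15 scores. Most of the listed deviations arise after enrolment, so they can be related to how the patient is doing. Following 11.8 would then discard observed primary-endpoint data on grounds that may not be independent of outcome.

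**Working it through.** The plan gives no figure to reproduce: the sample size of at least 50 comes with no effect size, power or deviation rate. The check is therefore mainly textual.

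**Step 1. Is there a rule that settles the conflict?**

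| Section | What it covers | Settles it? |
|---|---|---|
| 9.3 | Replacing statistical methods | No |
| 9.4 | Missing data not replaced or considered | No |
| 9.6 | ITT and safety sets only; no per-protocol set | No |
| 9.10 | Data queries and sensitivity to uncorrectable errors | No |
| 11.8 | Exclusion rule; no classifier named, no deadline | No |
| 11.9 | Counts of deviations in the report | No |

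**Step 2. Whom does 11.8 remove that 9.4 does not?** A patient with no Day 15 score is out of the Day 15 analysis under either rule. The part specific to 11.8 is patients with a Day 15 score and a significant deviation. Two routes follow directly from the text:

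- A patient with a recorded Day 15 score who missed another visit. This includes a patient complete to Day 15 who misses Day 29.
- A patient who met a withdrawal criterion in 5.3 but stayed in. Criterion 5 ("AE/SAE that requires an examination and/or treatment that would affect the study procedures significantly") and criterion 8 ("The patient receives/needs an additional treatment that could affects result of the study or the patient safety") are both broad. Had such a patient been withdrawn, any later loss of data would come from 5.3 and 9.4, not from 11.8.

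**Step 3. Illustrative size of the missed-visit route.** The inputs are n = 50 (stated minimum) and six scheduled post-baseline visits in Table 1 (Days 3, 5, 7, 11, 15, 29). The per-visit miss probability p and independence between visits are assumptions.

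- Missing Day 15, so already out under 9.4: 50 × p.
- Day 15 seen but at least one of the other five missed, so out only under 11.8: 50 × (1 − p) × [1 − (1 − p)^5] = 50 × [(1 − p) − (1 − p)^6].

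| p | Out under 9.4 | Out only under 11.8 |
|---|---|---|
| 1% | 0.5 | 50 × (0.990 − 0.9415) = 2.4 |
| 2% | 1.0 | 50 × (0.980 − 0.8858) = 4.7 |
| 5% | 2.5 | 50 × (0.950 − 0.7351) = 10.7 |
| 10% | 5.0 | 50 × (0.900 − 0.5314) = 18.4 |

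Missed visits may be rare in hospital, and 6.2 allows remote contact after discharge, so the low rows may be the more realistic.

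**Step 4. Can the direction be known?** Suppose all 50 have a score and 30 (60%) are in categories 1–2 at Day 15. Both the share and the removal rates are assumed, and this split is not the primary endpoint, which is the ordinal status compared with baseline.

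- Remove 10% or 20% of those 30 only: 27/47 = 57.4% or 24/44 = 54.5%.
- Remove 10% or 20% of the other 20 only: 30/48 = 62.5% or 30/46 = 65.2%.
- Remove 10% of both: 27/45 = 60.0%, no shift.

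For assumed shares of 40% to 80%, the one-sided shift is about 2 to 3 points at 10% removal and 3 to 6 points at 20%. The sign depends entirely on who deviates, and the documents do not say.

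**The case against.** The best defence is that *main* in 9.7.2 leaves room for a second efficacy analysis, so 11.8 can be read as an implied per-protocol analysis that leaves ITT in charge. That may have been the intention. But 11.8 speaks of the final efficacy analysis without qualification, and 9.6 defines no set to which it could apply.

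There are safeguards. Under 11.8 deviations are recorded and significant ones go to the ethics committee; under 11.9 the report gives their number. This leaves a trail that would make selective exclusion visible. It does not fix who classifies, or when.

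The size objection also stands. The 95% Wilson interval around 30/50 is about 46% to 72%, so the shifts in Step 4 lie well inside sampling error. With no control group, they would move a descriptive proportion and not a treatment comparison.

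Two stronger readings are tempting. A reader might infer that early recoverers who miss injections after discharge would be struck out. Section 11.8 does not name a missed dose, and no section says that one is an administration violation. A reader might also see a contradiction with 5.4, which keeps patients who stop the drug early under observation. That follows only if stopping early is a deviation, and 11.8 does not list it.

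**Conclusion.** The conflict is certain on the text. Section 11.8, followed as written, takes out of the efficacy analysis patients whom 9.6 and 9.7.2 put in, with no per-protocol set, no order of precedence and no classification made before outcomes are known.

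Its reach is limited to patients with both an observed Day 15 score and a significant deviation. How many that would be is not stated. Step 3 gives about 2 to 18 of 50 for assumed miss rates of 1% to 10%, and counts only the missed-visit route.

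A reader might infer that the rule flatters the drug, or that it penalises it. The documents support neither: direction and size cannot be determined from them, and Step 4 rests on assumed, one-sided removal. The point is that the main efficacy population is left open, not that a bias has been shown.

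**What to change.** 1. **Section 11.8.** State that significant deviations after enrolment do not remove a patient from the main (ITT) efficacy analysis, except where valid written consent is absent. The exception matters because 11.8 counts procedures without consent as a significant deviation, and 6.3.1 requires consent before any procedure.
2. **Section 9.6.** Add a per-protocol population for sensitivity analysis only. List the deviations that exclude from it, including ineligible enrolment. Name the role that classifies them, and require classification before the efficacy analysis is run.
3. **ITT definition.** Align 9.6 with 5.4, which drops undosed patients, for example as all enrolled patients who consented and received at least one dose.

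The cost is a few sentences and one extra sensitivity analysis; deviations are already recorded. Because the change affects the scientific value of the study, 11.7 requires local ethics committee approval of the amendment. The main result will include patients with deviations, which is what the ITT choice in 9.7.2 already implies.

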11.9. Final study report

A medical research expert/medical consultant will be involved in preparation of the observational study report. The discussion of the results and conclusions will include a clear conclusion on the safety profile as well as efficacy of the investigational products.

The observational study report will show the number and type of Protocol Amendments (if applicable), the number of violations and deviations from the Protocol found during the study.

The final version of the report will be signed by the ones who prepared it, a medical research expert/medical consultant, the head of this study, and will be approved by the head of the institution and certified with the seal of the institution.

